placed on fetal head area. Middle cerebral arteries (MCA) run anteriorly on both sides of the ring of cerebral arteries at the position of the double head diameter (see Figure 1A). We can get waveforms of MCA examined by pulsed wave doppler (see Figure 1B). The probe was placed at the placenta area, and we can see the fetal umbilical cord connecting to the center of the placenta. Umbilical artery (UA) could be identified by color flow, and its waveforms were examined by pulsed wave doppler (see Figure 1C and 1D). The probe was placed at the midpoint of the groin. The right and left uterine arteries (UtA) could be identified by color flow at the apparent crossover with the external iliac arteries, and pulsed wave doppler was used to obtain waveforms (see Figure 1E and 1F). 3 to 10 arterial spectrograms with clear edges and no background noise at baseline were selected. The above arterial blood flow indexes were measured three times and the average value was taken. The S/D、PI、RI value of MCA、UA、UtA can be measured automatically by ultrasound instrument. All doppler examinations were performed by the same sonographer.

5. Primary outcomes

The main indexes were doppler blood flow indexes (S/D, PI, RI value) of UtA, UA, MCA before analgesia (T_0) and 30 min (T_1), 60min (T_2), 90 min (T_3) after analgesia in the three groups.

6. Secondary outcomes

Fetal heart rate (FHR) and mean artery pressure (MAP) at T_0 , T_1 , T_2 and T_3 , neonatal weight, time of each stage of labor, rate of midwifery, neonatal umbilical artery blood gas index and Apgar score at 1 min, 5 min, 10 min after birth of the three groups were included in the secondary indicators.

7. Statistical Analysis Plan

In this study, SPSS 13.0 was used for statistical analysis, and GraphPad Prism 8 was used for mapping. Measurement data were expressed as mean \pm standard deviation ($\bar{x}\pm s$), and categorical data were expressed as frequency, percentage, or rate. Paired t

test was used for intra-group comparison and independent sample t test was used for inter-group comparison of measurement data conforming to normal distribution. The measurement data with non-normal distribution were analyzed by rank sum test. Chi-square test was used for statistical analysis of categorical data. $P < 0.05$ indicates statistical significance.

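### Section 7 gives no longitudinal method or T1–T3 summary, so a sustained arm difference is estimated less precisely than it could be and no test supports a claim that a difference appears or fades

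*Combined protocol and SAP*

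**What the plan says.** Section 5 makes the primary outcomes the Doppler indices "S/D, PI, RI value) of UtA, UA, MCA before analgesia (T_0) and 30 min (T_1), 60min (T_2), 90 min (T_3) after analgesia", in three arms. That is nine indices (three measures in each of three vessels) at one baseline and three later times. Section 6 puts FHR on the same schedule, together with "mean artery pressure (MAP) at T_0" and the later times.

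Section 7 is the whole analysis plan. For continuous data it gives a paired t test within arms, and between arms "independent sample t test was used for inter-group comparison of measurement data conforming to normal distribution". Otherwise, "The measurement data with non-normal distribution were analyzed by rank sum test". It names no repeated-measures or mixed model, no arm-by-time term, and no average or area under the curve over T1–T3. The only averaging described is in section 4, where three readings of an index are averaged. That reads as replicate readings within one examination, not averaging over the 30, 60 and 90 minute scans.

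**The concern.** A two-sample t test or rank sum test uses one number per woman. With no summary defined, the natural way to apply section 7 is one test at each time for each pair of arms. Two things follow.

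- **Precision.** If an arm difference persists from 30 to 90 minutes, three scans per woman carry more information about it than one. The listed tests do not use it.
- **Change over time.** Whether an arm difference grows or fades is a question about differences between times. The paired tests link T0 to a later scan, but only within an arm, so they do not compare arms. With only separate P values to hand, a reader who sees significance at T1 and not at T3 may conclude that the effect wore off, and the plan has no test to confirm or refute that.

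This is separate from the number of tests. A multiplicity correction would neither recover the precision nor supply an arm-by-time test.

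**Working it through.** **Inputs from the documents:** 30 women per arm (section 2); three post-analgesia times (section 5); significance level 0.05 (section 7, taken as two-sided because sidedness is not stated). The plan gives no SD, effect size, power or sample-size calculation, so there is no figure of its own to reproduce.

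**Assumptions, for scale only:** equal correlation r between any two of a woman's T1–T3 values, with r from 0.3 to 0.8; equal SD at each time; effects in SD units; two arms compared; no T0 adjustment.

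**1. Sustained difference of 0.5 SD.**
- Variance of the mean of three equally correlated values, in SD² units: (1 + 2r)/3.
- SE ratio to a single time: √[(1 + 2r)/3].
- Equivalent women per arm for a single-time test: 30 ÷ [(1 + 2r)/3] = 90/(1 + 2r).
- Noncentrality at a single time: 0.5 × √(30/2) = 1.94. On 58 degrees of freedom this gives power of 47.8%. For the average, divide 1.94 by the SE ratio.

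| r | Variance | SE ratio | Equivalent n per arm | Noncentrality | Power, average | Power, one time |
|---|---|---|---|---|---|---|
| 0.3 | 0.533 | 0.73 | 56 | 2.65 | 74% | 48% |
| 0.5 | 0.667 | 0.82 | 45 | 2.37 | 65% | 48% |
| 0.7 | 0.800 | 0.89 | 37.5 | 2.17 | 57% | 48% |
| 0.8 | 0.867 | 0.93 | 34.6 | 2.08 | 53% | 48% |

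**2. Reading a time course from separate P values.** Two arms were simulated exactly 0.5 SD apart at T1, T2 and T3, so nothing appears or fades (20,000 trials per r).

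| r | Some times significant, others not | Significant at T1, not at T3 |
|---|---|---|
| 0.3 | 60% | 20% |
| 0.5 | about 50% | 17% |
| 0.7 | 38% | 13% |

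**3. Waning difference of 0.6, 0.4 and 0.2 SD.**
- T1 alone: noncentrality 0.6 × √15 = 2.32, power 63%.
- Average: mean difference (0.6 + 0.4 + 0.2)/3 = 0.4 SD, so 0.4 × √15 = 1.55 divided by the SE ratio. Power is 55%, 46% and 40% at r = 0.3, 0.5 and 0.7.
- Arm-by-time test for two arms: squared deviations from the mean difference sum to 0.04 + 0 + 0.04 = 0.08. Noncentrality is 15 × 0.08/(1 − r) = 1.2/(1 − r), or 1.71, 2.40 and 4.00. On 2 and 116 degrees of freedom, power is 19%, 26% and 41% at r = 0.3, 0.5 and 0.7.

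The average therefore helps when the effect is sustained and hurts when it is short-lived. The interaction test is the right one for waning, but it is weak at this sample size.

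**The case against.** The strongest reply is that comparing arms at each time is a legitimate reading of section 5, which lists values at stated times. Taken as a method, each such test is valid for that time's difference. With complete data, an unstructured covariance and no T0 adjustment, a mixed model gives essentially the same time-specific differences. The precision gain comes only from averaging, which answers a different question and pays off only if the effect is sustained. Section 3 gives the arms different intrathecal injections and then the same epidural solution, so waning is at least as plausible. No stated objective concerns onset or offset. All of this stands, and it limits the point to an improvement in method.

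Three stronger readings are tempting and are not supported:

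- A reader might infer that the per-time tests are wrong. They are not. They are less efficient for a sustained effect and say nothing about change over time.
- A reader might infer that the plan forbids combining the scans. Section 7 never says that tests are done at each time. This follows only from the kind of test named and the absence of any summary. An unstated t test on change from T0 is conceivable, but it too would handle one later time at once.
- A reader might infer that missing scans leave different women compared at T1, T2 and T3. The documents give no missing-scan rate, and section 1 already excludes women who could not cooperate with ultrasound, so this cannot be a main reason.

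What survives is that three repeated scans per woman are collected and no between-arm method uses them together.

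**Conclusion.** The point holds as a gap in specification: section 7 has no longitudinal method and no T1–T3 summary for the nine primary indices, MAP or FHR. The missing arm-by-time test does not depend on any assumed figure.

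The size of the precision loss does. For a sustained difference, the SE of the average is 0.73 to 0.93 of the single-time SE at r from 0.3 to 0.8. For a constant 0.5 SD that is power of 74% down to 53%, against 48%, so the gain is modest at the high end of r. The risk of a misleading time-course reading, 13–20% for significance at T1 but not at T3, rests on the same equal-correlation assumption with r from 0.7 to 0.3. That such a reading would be made is a possibility, not something the plan states.

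This is a worthwhile, inexpensive improvement and not a flaw that invalidates the planned comparisons.

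**What to change.** In section 7, analyse each Doppler index, MAP and FHR with one linear mixed model:

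- outcome values at T1, T2 and T3, with T0 as a covariate;
- arm (three levels), time and arm × time;
- unstructured within-woman covariance;
- a transformation, for example log, for skewed indices, in place of the rank sum test.

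For each of the three arm pairs, report the T1–T3 average difference and the three time-specific differences, with confidence intervals. Allow a statement that a difference appears or wanes only from the arm × time contrast. State that a non-significant interaction is not evidence of a constant effect.

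**Cost.** SAP wording and somewhat more analysis work; no new data.

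**Downsides.** The average dilutes a short-lived effect: about 40–55% power against 63% at T1 alone in the waning case above, which is why the time-specific estimates stay. The interaction test has only about 19–41% power in that case at r = 0.7 or below, so much real waning would go undetected. The full report also contains 9 indices × 3 pairs × 4 estimates = 108 primary contrasts, against 9 × 3 × 3 = 81 time-by-time tests. Choosing a primary contrast and controlling multiplicity still have to be settled separately.
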